### 3) Question to evaluate the physician experience in treating patients presenting with painful muscle contractures:

- Number of prescriptions (not patients) of systemic (oral and/or intramuscular) thiocolchicoside containing medicinal products written within the last 12 months

The following information will also be assessed:

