**Table 9.5.2–1: Sample size obtained for various precisions and proportions**

Margin of error for 95% CI				
Proportion	5%	4%	3%	2%
10%	139	216	384	864

30%	323	504	896	2,017
50%	384	600	1,067	2,401
70%	323	504	896	2,017
90%	139	216	384	864

Since the proportion of physicians informed about the updated prescribing conditions and recommendations for safe use of systemic thiocolchicoside is not known and there is no evidence supporting the expected proportion, the worst case hypothesis will be assumed considering that 50% of physicians will have received and understood the safety information distributed recently. This assumption yields the largest sample size.

Considering this hypothesis and in order to achieve a CI of 95% with a half-width of 4%, a total of 600 analysable physician questionnaires will be needed for the overall sample. Considering a margin of error of 5% (or 3% respectively) instead of 4%, the required sample size would be 384 (or 1,067) analysable physician questionnaires for the overall sample.

Based on IMS Medical Radar experience from previous similar surveys and estimates and the evaluation of the survey feasibility with four countries, the sample size of 600 is considered for this study. Indeed, the elected sample size should be sufficient to be divided between 4 countries and further between 3 groups of specialities.

It is estimated that about 30% of physicians will not complete the questionnaire until the end or not be analysable (i.e. physicians who respond to questions regarding their knowledge on the updated safety concerns of systemic thiocolchicoside or physicians without any prescription of systemic thiocolchicoside in the last 12 months or physicians who have to interrupt the interview due to an emergency (rare)). Taking into account these respondent physicians without analysable questionnaires, the overall sample size of 780 participating physicians will be required to reach 600 analysable questionnaires (i.e. recruitment of physicians should continue until 600 analysable questionnaires have been reached).

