**Table 9.5.2–4: Sample size per country and per specialty**

n (vertical % per country)*	France	Greece	Italy	Portugal	All
Number of physicians with an analysable questionnaire	180	120	180	120	600
GPs	90 (50.0%)	60 (50%)	90 (50.0%)	60 (50%)	300 (50%)
Rheumatologists	40 (22.2%)	30 (25%)	40 (22.2%)	30 (25%)	140 (23.3%)
Orthopedists / orthopaedic surgeons	50 (27.8%)	30 (25%)	50 (27.8%)	30 (25%)	160 (26.7%)
Number of participating physicians required	234	156	234	156	780
GPs	117 (50%)	78 (50%)	117 (50%)	78 (50%)	390 (50%)
Rheumatologists	52 (22.2%)	39 (25%)	52 (22.2%)	39 (25%)	182 (23.3%)
Orthopedists / orthopaedic surgeons	65 (27.8%)	39 (25%)	65 (27.8%)	39 (25%)	208 (26.7%)

\* To be aligned with the n by country, numbers n per specialty have been rounded to the most closed integer.

Since the relative weight of each country and of each specialty in the sampling plan is different from its real relative weight in estimations, the extrapolation of the raw survey results to the overall target population would not be relevant.

A sample adjustment will be performed. The survey results will be weighted to reflect the real proportion of the four countries and within each country to reflect the real proportion of each specialty in order to extend the survey results to the overall target population. Both unweighted (i.e. raw data) and weighted results will be presented in the report.

A weight variable will be applied to each statistical unit (i.e. the analysable physician) during the results calculation in order to correct any over-or under-sampling that may have occurred for a country or specialty. This weight variable will indicate how many unit(s) of the population of interest an observation will count in a statistical procedure. Its value will change per country and per specialty. The weights will be normalised to obtain their sum equal to the sample size.

In order to fill-in each stratum of the sample survey from the IMS OneKey reference files, an independent sample will be selected per stratum through a simple random sampling without replacement.

In each specific stratum, physicians will be contacted according to the order of draw in this stratum. If a physician does not want to participate in the survey, the next one in order of

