### **Sample of collected prescriptions:**

For the data on prescriptions, the statistical unit considered will be the individual drug prescription to patient. Although the level of contribution to this section per interviewed physician is not known and will depend both on the market sells of systemic thicolchicoside in each country and for each specialty, and on the percentage of interviewed physicians who prescribed the drug to patients. Physicians are requested to report up to 5 last prescriptions of systemic thicolchicoside written over the last 12 months before the survey, each pertaining to a unique patient.

As a result, the sampling method (systematic sampling) is expected to allow generalisability of results once the overall sample of physicians can be shown to be generalisable.

Based on IMS Medical Radar experience from previous similar surveys, it is estimated that in average each interviewed physician who prescribed systemic thicolchicoside to patients will contribute with 3 prescriptions on average.

If a conservative rate of 50% is assumed to evaluate the part of interviewed physicians who prescribed systemic thicolchicoside to patients, the sample size for prescriptions will be about 900, thus largely sufficient for the study of proportions of appropriate use of drug under the same assumptions of confidence interval and precision as described above.

Note that a sample adjustment will be also implemented for the sample of collected prescriptions using the same methodology as for analysable questionnaires but with different weights.

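### Capping reports at five prescriptions per physician and weighting only by stratum yields a capped-count average, so the claim that prescription results generalise once physicians do is not justified

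*Protocol*

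**What the plan says.** Section 9.5.2 (Sample of collected prescriptions) states that "the statistical unit considered will be the individual drug prescription to patient". Physicians are asked for "up to 5 last prescriptions of systemic thicolchicoside written over the last 12 months before the survey, each pertaining to a unique patient", and each contributing physician "will contribute with 3 prescriptions on average". The section calls this systematic sampling and expects prescription results to generalise once the physician sample has been shown to do so.

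The adjustment is applied to the "sample of collected prescriptions using the same methodology as for analysable questionnaires but with different weights". The questionnaire weight, defined after Table 9.5.2–4, corrects over- or under-sampling of a country or specialty: "Its value will change per country and per specialty". Section 9.7.1 likewise weights by specialty and country. No values or formula are given for the different prescription weights.

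Section 9.3, item 3, collects from every physician the "Number of prescriptions (not patients) of systemic (oral and/or intramuscular) thiocolchicoside containing medicinal products written within the last 12 months". It is listed as a measure of experience, and no part of the protocol uses it in weighting.

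**The concern.** Physicians are drawn by simple random sampling within a stratum, so each physician in a stratum has the same chance of selection. Their prescriptions do not. If one physician wrote 200 in the year and another wrote 6, and each reports 3, the sampling fractions are 3/200 = 1.5% and 3/6 = 50%, yet both sets of reports carry the same stratum weight. A physician who reports 5 also counts five times as much as one who reports 1.

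A representative sample of physicians therefore does not produce a representative sample of prescriptions. If appropriate use differs between high- and low-volume prescribers, the weighted percentage will differ from the share of prescriptions that were appropriate. Section 7.2 relies on these details for pregnancy, lactation and contraception, which it says databases rarely record.

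**Working it through.** **1. The plan's own figure.** The base is "a total of 600 analysable physician questionnaires will be needed for the overall sample": 0.5 × 0.5 × 1.96² / 0.04² = 600. With the 50% contributing share assumed in 9.5.2 and 3 prescriptions each, 600 × 0.50 × 3 = 900, which matches the stated figure of about 900.

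**2. Does the cap bind?** Prescriptions come from Table 7.2–1 (in thousands there) and physicians from Table 9.5.2–2.

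| Stratum | Prescriptions per year | Physicians | Mean per physician | 5 as share | 3 as share |
|---|---|---|---|---|---|
| French GPs | 2,981,504 | 90,630 | 32.9 | 15.2% | 9.1% |
| French rheumatologists | 73,152 | 2,353 | 31.1 | 16.1% | 9.6% |
| Italian GPs | 1,365,608 | 45,203 | 30.2 | 16.6% | 9.9% |
| Italian orthopaedists | 388,895 | 9,234 | 42.1 | 11.9% | 7.1% |

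The denominators are all listed physicians. Only those who prescribed within 12 months are eligible (9.2.1), so the mean among eligible physicians is at least this high.

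**3. What is estimated.** Within a stratum, let physician i write v prescriptions in the year, report r of them (1 to 5), and have probability p that a prescription is inappropriate.

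- Planned estimate: Σ(r·p) / Σr. A weight constant within the stratum multiplies numerator and denominator alike and cancels.
- Proportion among prescriptions written: Σ(v·p) / Σv.

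The two agree if, across reported prescriptions, v/r is uncorrelated with p. Otherwise they differ, whatever value the stratum weight takes.

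**4. Possible size (assumed inputs).** The documents give neither the spread of volume nor its link to appropriateness. Assume log-normal volume with mean 33; r equal to the smaller of v and a uniform draw from 1 to 5 (mean 3, as planned); and logit p = logit(0.25) + b × standardised log-volume. The odds ratio per SD is exp(b). Gaps come from unrounded values.

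| Log-SD of volume | Odds of inappropriate use per SD | Among prescriptions written | Planned estimate | Gap (points) |
|---|---|---|---|---|
| any | no link | 25.0% | 25.0% | 0 |
| 1.0 | 1.11 times higher | 27.0% | 25.1% | 1.9 |
| 1.0 | 1.35 times higher | 31.4% | 25.6% | 5.8 |
| 1.0 | 1.65 times higher | 36.2% | 26.3% | 9.9 |
| 1.0 | 1.65 times lower | 17.9% | 25.7% | −7.8 |
| 1.3 | 1.65 times higher | 39.7% | 27.0% | 12.8 |
| 1.3 | 1.65 times lower | 15.8% | 25.0% | −9.1 |

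With a median rate of 75% instead of 25% the signs mirror, so about 13 points is possible in either direction.

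**5. Price of volume weighting.** With weights v/r and no trimming, the Kish effective size is about 45% of the number reported at log-SD 0.7 and 27% at 1.0. For 900 prescriptions:

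- 900 × 0.45 = 405, half-width 1.96 × √(0.25/405) = 4.9 points
- 900 × 0.27 = 243, half-width 1.96 × √(0.25/243) = 6.3 points

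Without this weighting the half-width is 1.96 × √(0.25/900) = 3.3 points. All three ignore clustering within physician.

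**The case against.** **The weights are unspecified, and a formula can be left to the analysis plan.** It is true that no values are given. They might be stratum prescription totals, which would correct between strata: by physicians France is 58.8% of the four countries, by prescriptions 3,072.412 / 5,845.896 = 52.6%. But the protocol names the method and draws the inference itself, and a stratum-level weight of any value leaves the within-stratum problem in place.

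**The section is secondary and already carries a caution.** The objective in 8.2 is a proportion of physicians, and 9.9.4 asks for cautious interpretation of the prescription data. This limits the importance of the point. That caution, however, concerns recall and the choice of memorable patients. It does not mention the cap or unequal sampling fractions, which, unlike recall bias, can be examined with data already collected.

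**The size is assumed.** This stands. The range starts at zero, and a weak link gives a small gap.

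**Volume weighting is not a clean remedy.** This stands too. The 12-month count is of prescriptions, while the reported items are one per patient, so repeat prescriptions raise the numerator but cannot appear as separate reports. The count is self-reported, and the loss of precision would miss the 4-point half-width that the protocol says 900 prescriptions comfortably support. Trimming brings back some of the bias.

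Two stronger readings are tempting. A reader might infer that the planned figure is an average over physicians. It is not: the prescription is the unit, and a physician counts in proportion to the number reported. It merely lies close to the physician average in these scenarios because volumes far exceed five. A reader might also infer that the figure is meant to be set beside the drug utilisation study. The protocol calls the survey a complement to that study and plans no such comparison.

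**Conclusion.** The point holds as a mismatch between what the design delivers and what 9.5.2 claims for it. The planned result describes up to five recent prescriptions per physician, weighted by stratum. It is not the proportion of prescriptions written, and its generalisability does not follow from that of the physician sample. This rests on reading the same methodology as a weight constant within country and specialty, which is what the protocol's definition says.

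No bias has been shown. It is zero if appropriateness is unrelated to volume within a stratum. Otherwise the assumed log-normal scenarios give up to about 13 points, with a sign the documents cannot settle. The size of the loss in precision and the uncertain quality of the volume count argue against making a volume-weighted figure the main result.

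**What to change.** In 9.5.2 and 9.7.1:

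- Delete or qualify the sentence that prescription results generalise once the physician sample does.
- Label the planned figure as a proportion among up to five recent prescriptions per physician, and state what the different weights are.
- Beside the planned weighted and unweighted results, add a sensitivity analysis that weights each prescription by stratum weight × (reported 12-month prescriptions / number reported), with extreme weights trimmed by a rule set in advance.
- State its limits: self-reported volume, prescriptions set against unique patients, and wider intervals (effective size about 27–45% of the number reported at assumed log-SD 1.0–0.7, before trimming).

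The cost is a few sentences and some analysis programming. No question needs adding, because the 12-month count is already asked. The planned results stay as they are, so their precision is unaffected; only the sensitivity result carries the wider interval.

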## **9.6 DATA MANAGEMENT**

The survey will be conducted according to the Standard Operating Procedures (SOPs) of IMS Medical Radar and IMS Real World Evidence Solutions.

Collected data will be entered and stored in a database specific to the survey and the country. A study database will be created by merging of databases of each country.

Data will be checked in terms of consistency before data analysis:

- removal of duplicates (if required),
- data labelling and data formatting,
- range and consistency checks for each variable to identify potential non admissible values,
- cross-check the consistency of data for related variables (if feasible).

The number of variables with missing values will be indicated. Missing values are excluded from the calculation of percentages.  
The study database will be locked once validated.

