#### Handling of missing data:

The number of missing data will be indicated. Missing data will not be replaced by imputation methods. They are expected to be few and distributed at random.

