### 9.7.3 Questionnaire analysis

The general statistical considerations described above (§9.7.1) will be applied for quantitative and qualitative variables. The number of missing data will be indicated. Missing values are expected to be few and distributed at random. Since there is no applicable method unanimously accepted, there will be no replacement or imputation of missing data (13).

Confidence intervals of 95% will be evaluated for endpoint variables.

Physicians' answers will be analysed by subgroups of physician's specialty per country, and on the overall dataset.

For each question associated to the outcomes included in the main objective, a criterion will be calculated to separate physicians with an appropriate answer (or at least one appropriate response if the corresponding question allows multiple answers or is an open-ended question). These proportions of appropriate answers will be expressed among physicians with complete web-questionnaires.

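### The proportion correct is computed among completers only, on an unsupported missing-at-random assumption, with no split of the 30% expected losses and no bound on a possible upward bias

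*Protocol*

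**What the plan says.** The protocol fixes four things that act together.

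- **Item level.** Section 9.6 (Data management): "Missing values are excluded from the calculation of percentages".
- **Justification.** Under Handling of missing data in Section 9.7.1, nothing is imputed, and of the missing data it is said: "They are expected to be few and distributed at random". Section 9.7.3 repeats this ("Missing values are expected to be few and distributed at random") and adds that no imputation method is unanimously accepted.
- **Denominator.** Section 9.7.3: "These proportions of appropriate answers will be expressed among physicians with complete web-questionnaires". Section 9.7.1 likewise uses complete analysable questionnaires.
- **Expected losses.** Section 9.5.2: "It is estimated that about 30% of physicians will not complete the questionnaire until the end or not be analysable". The reasons listed there include "physicians without any prescription of systemic thiocolchicoside in the last 12 months" and interruption by an emergency, described as rare. They also include, as printed, "physicians who respond to questions regarding their knowledge on the updated safety concerns of systemic thiocolchicoside". Recruitment continues until 600 analysable questionnaires are in hand, from 780 participants.

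Other sections describe the losses. Section 9.7.2 defines a cooperation rate and seeks reasons for non-response. Section 9.8.2 counts the non-analysable questionnaires. Sections 9.7.1 and 9.9.2 compare respondents with non-respondents on available characteristics.

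**The concern.** Section 8.2 asks for the proportion of targeted physicians who understood and implemented the restrictions. The estimate describes those who reached the end of the questionnaire. The two agree only if eligible physicians who stop or skip know as much as those who finish. In a knowledge survey that cannot be taken for granted, because a blank or an exit may itself be a sign of not knowing. If it is, the completers' proportion is too high, which flatters the risk minimisation measures.

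Three features make this hard to see afterwards:

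- Recruiting until 600 analysable questionnaires are reached means the final sample size does not reveal the selection.
- The 30% has no split. Physicians with no prescription in 12 months fail the inclusion criterion in Section 9.2.1 and are rightly left out. Eligible physicians who break off belong to the target population.
- The printed definition classes physicians who answer the knowledge questions as non-analysable. Presumably a negation has been lost. With it restored, being analysable depends on having answered the very items that form the outcome.

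**Working it through.** **Inputs from Section 9.5.2:** expected proportion P = 0.50, half-width e = 0.04, 95% confidence (z = 1.96), 600 analysable questionnaires, 780 participants. **Not given in the protocol:** the share of the non-analysable who are eligible, and how much they know. Both are assumed below and varied. All proportions are unweighted.

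**1. The plan's own figure.** n = P(1−P)z²/e² = 0.25 × 1.96² / 0.04² = 600.2, which reproduces 600. The planned non-analysable number is 780 − 600 = 180.

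**2. Bounds around 50%.** Let E be the number of eligible physicians among the 180. With 300 of 600 completers correct:

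- lower bound (all E not appropriate) = 300/(600 + E)
- upper bound (all E appropriate) = (300 + E)/(600 + E)

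| Assumed eligible share of the 180 | E | Lower | Upper |
|---|---|---|---|
| 25% | 45 | 300/645 = 46.5% | 345/645 = 53.5% |
| 50% | 90 | 300/690 = 43.5% | 390/690 = 56.5% |
| 100% | 180 | 300/780 = 38.5% | 480/780 = 61.5% |

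The last row is an outer limit, since the protocol says that some of the losses are non-prescribers.

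**3. When the bound passes the planned margin.** 0.5E/(600 + E) > 0.04 gives E > 24/0.46 = 52.2. So 53 eligible physicians, or 53/180 = 29% of the non-analysable, are enough.

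**4. A less extreme assumption.** If eligible non-completers are correct 20 percentage points less often than completers (assumed), the upward bias is 0.20 × E/(600 + E). That is 1.4 points at E = 45, 2.6 at E = 90 and 4.6 at E = 180. If they do not differ, it is 0.

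**5. Blanks among completers.** If a share m of answers to an item is missing and these are counted as not appropriate, an observed 50% becomes 50% × (1 − m). That is 49.0%, 47.5% and 45.0% at assumed m of 2%, 5% and 10%.

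**6. A higher observed proportion.** At 80% correct (480 of 600) and E = 90, the bounds are 480/690 = 69.6% and 570/690 = 82.6%. The interval is lopsided because the worst case has more room below a high proportion.

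**Side note.** 780 is 600 × 1.30, which implies a loss of 180/780 = 23.1%. A literal 30% loss would need 600/0.70, or 858 participants, leaving 258 non-analysable. With all of those eligible, the bounds around 50% widen to 35.0–65.0%. The inflation step is a separate matter.

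**The case against.** A reader might infer that the protocol contradicts itself, with few missing values in one place and 30% lost in another. It does not. The statement about few and random concerns missing values, whereas the 30% concerns whole questionnaires, including non-prescribers and rare emergencies. Few blanks among completers is compatible with 30% attrition.

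A reader might also take the upward bias as established. The documents contain no data on whether physicians who stop know less. Length is another plausible reason for leaving: Sections 9.4 and 10.2.1 give 10 to 15 minutes plus about 5 minutes for each of up to five prescriptions, so up to 40 minutes. The worst case alone also overstates the problem, since the bounds run both ways and the lower one assumes that no eligible non-completer would have answered appropriately.

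The questionnaire is a separate document, so it cannot be seen whether items are mandatory or offer a don't-know option. A ticked don't-know is an answer and already fails the criterion in Section 9.7.3. It is also only one reading that the general sentence in Section 9.6 removes blanks from the endpoint denominator. The study is descriptive and states no success threshold. Scoring every blank as wrong in the main analysis would replace one untestable assumption with another.

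Those points stand, and they limit the claim. Two counter-arguments carry less weight. The counts, rates and respondent comparisons describe the losses but neither change nor bound the knowledge estimate. A sensitivity table could be left to an analysis plan not shown here, but the protocol itself fixes the denominator, the justification and the faulty definition.

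**Conclusion.** The point holds in a limited form. The protocol fixes a completers-only denominator, removes missing values from percentages and gives an unsupported assumption as the reason. Eligible break-offs cannot be told apart from ineligible physicians within the expected losses. Upward bias is plausible, but neither its existence nor its size is shown.

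The possible effect is large against the stated precision: the bounds around 50% exceed 4 points once about 29% of the 180 are eligible. With an assumed 20-point knowledge gap, the bias is 1.4 to 4.6 points for eligible shares from a quarter to all. These figures rest on the planned 600 of 780 and on assumed shares. The documents do not support a stronger conclusion, such as a definite bias or a need to replace the completers result as the main analysis.

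**What to change.** - In Section 9.5.2, correct the definition of non-analysable so that it refers to physicians who do not respond to the knowledge questions.
- Report screen failures (no prescription in 12 months, other exclusions) separately from eligible physicians who break off after passing the screener. List break-offs before the screener as eligibility unknown.
- Keep the completers result. For each knowledge item, add a sensitivity analysis among all eligible physicians who started, with blanks and break-offs counted as not appropriate, together with the opposite bound.
- Delete the statements in Sections 9.7.1 and 9.7.3 that missing data are few and random as the justification. State instead that the mechanism is unknown and is addressed by the bounds.

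**Cost:** one extra table and a lower figure that may look less favourable. No new data collection should be needed, because Section 9.8.2 already identifies non-analysable questionnaires in the study database and Section 10.3.2 says that entered data can be retrieved at any time.
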